## 3) History of biological treatment of JIA

Presence/absence of history of biological therapy, name of drug, dose, duration (start date and end date), and reason for discontinuation.

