## 9. General agreements concerning analysis

### 9.1. Handling of missing data

Missing data will not be complemented, etc. during analysis. However, input data need to be complemented for some items. For the input data requiring complement, the complement methods are defined in the definition of each item in Chapter 10 and subsequent chapters.

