### 9.2. Handling incomplete dates

Missing dates should be treated as “unspecified”. Dates including unknown date, month or year, or dates that cannot be true according to the calendar should be handled as “unknown” without exception.

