Administration by a doctor	In “2. Status of Humira treatment” in the registration form, administration is “administration by a doctor” at all timings.
Dosage and administration category: Dose increase group (20 mg → 40 mg)	In “2. Status of Humira treatment” in the registration form, “dose” was increased from 20 mg to 40 mg.
Dosage and administration category: Maintained dose group	In “2. Status of Humira treatment” in the registration form, “dose” was never increased or reduced.
Dosage and administration category: Other	In “2. Status of Humira treatment” in the registration form, “dose” was reduced to below 20 mg, “dose” was increased from 40 mg to 80 mg, “dose” was increased and then reduced, or “number of doses” is other than biweekly.
Patients deviated from	Patients who received Humira at a dose other than “20 mg/2 weeks”

Name of data	Derivation and calculation methods
recommended dosage and administration of Humira	or “40 mg/2 weeks” are defined as patients deviated from the recommended dosage and administration.
Previous medications	Of the drugs listed under “Status of administration of concomitant drugs” in “5. Previous medications for juvenile idiopathic arthritis” in the CRF and confirmed to have been administered between the start date of Humira treatment - 90 days and the start date of Humira treatment - 1 day, drugs falling under “MTX”, “DMARDs”, “steroid (oral + injection)” or “NSAIDs (oral + injection)” in “Drug code list_20171012.xlsx” are defined as previous medications.
Status of previous medications	“With previous medications” should be selected when the patient was previously treated with medications, “unknown/unspecified” should be selected when “Status of previous medications for juvenile idiopathic arthritis” is not specified or indeterminable, and “without previous medications” should be selected otherwise.
Previous medication: Methotrexate	“With previous medication: methotrexate” should be selected when the conditions for “previous medications” are met and the previous medication falls under “MTX” in “Drug code list_20171012.xlsx”, “unknown/unspecified” should be selected when the status of previous medications is “unknown/unspecified”, and “without previous medication: methotrexate” should be selected otherwise.

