Previous medication: Corticosteroid	“With previous medication: corticosteroid” should be selected when the conditions for “previous medications” are met and the previous medication falls under “steroid (oral + injection)” in “Drug code list_20171012.xlsx”, “unknown/unspecified” should be selected when the status of previous medications is “unknown/unspecified”, and “without previous medication: corticosteroid” should be selected otherwise.
Previous medication: NSAIDs	Drugs that meet the conditions for “previous medications” and fall under “NSAIDs (oral + injection)” in “Drug code list_20171012.xlsx”.
Previous medication: Other DMARDs	“With previous medication: other DMARDs” should be selected when the drug meets the conditions for “previous medications” and does not fall under “MTX” and falls under “DMARDs” in “Drug code list_20171012.xlsx”, “unknown/unspecified” should be selected when the status of previous medications is “unknown/unspecified”, and “without previous medication: other DMARDs” should be selected otherwise.
Previous medication (biological products)	Drugs listed in “4. History of treatment with biological products for juvenile idiopathic arthritis” (which applies to all biological products previously used) in the CRF should be all previous medications (biological products) confirmed to have been administered between the start date of a biological product and the start date of Humira

Name of data	Derivation and calculation methods
	treatment - 1 day. Alternatively, of the drugs listed under “Status of administration of concomitant drugs” in “5. Previous medications for juvenile idiopathic arthritis” in the CRF and confirmed to have been administered between the start date of Humira treatment - 90 days and the start date of Humira treatment - 1 day, drugs falling under “biological products” in “Drug code list_20171012.xlsx” are defined as previous medications (biological products).
History of treatment with previous medications (biological products)	“With a history of treatment with previous medications (biological products)” should be selected when the patient was previously treated with medications (biological products), “unknown/unspecified” should be selected when “History of treatment with biological products” is not specified or indeterminable, and “without a history of treatment with previous medications (biological products)” should be selected otherwise.

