Previous medication (biological product): tocilizumab	“With previous medication (biological product): tocilizumab” should be selected when the drug meets the conditions of “previous medications (biological products)” and the higher order 7 digits of the drug code of the previous medication (biological product) are “6399421”, “unknown/unspecified” should be selected when the history of treatment with previous medications (biological products) is “unknown/unspecified”, and “without previous medication (biological product): tocilizumab” should be selected otherwise.
Previous medication (biological product): etanercept	“With previous medication (biological product): etanercept” should be selected when the drug meets the conditions of “previous medications (biological products)” and the higher order 7 digits of the drug code of the previous medication (biological product) are “3999424”, “unknown/unspecified” should be selected when the history of treatment with previous medications (biological products) is “unknown/unspecified”, and “without previous medication (biological product): etanercept” should be selected otherwise.
Previous medication (biological product): other	“With previous medication (biological product): other” should be selected when the drug meets the conditions of “previous medications (biological products)” and the higher order 7 digits of the drug code of the previous medication (biological product) are other than “6399421” and “3999424” and the drug falls under “Biological products” in “Drug code list_20171012.xlsx”, “unknown/unspecified” should be selected when the history of treatment with previous medications (biological products) is “unknown/unspecified”, and “without previous medication (biological product): other” should be selected otherwise.
Concomitant drugs	Concomitant drugs are defined as drugs listed in “5. Previous medications for juvenile idiopathic arthritis”, “6. Status of

Name of data	Derivation and calculation methods
	administration of concomitant drugs (1) [Concomitant drugs for juvenile idiopathic arthritis]”, “6. Status of administration of concomitant drugs (2) [Other concomitant drugs]” in the CRF and confirmed to have been administered between the start date of Humira treatment and the end date of Humira treatment.

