Status of concomitant drugs	“With concomitant drugs” should be selected when the patient is treated with concomitant drugs, “unknown/unspecified” should be selected when “Status of previous medications for juvenile idiopathic arthritis/concomitant drugs for juvenile idiopathic arthritis/other concomitant drugs” is not specified or indeterminable, and “without concomitant drugs” should be selected otherwise.
Concomitant drug: methotrexate	“With concomitant drug: methotrexate” should be selected when the conditions for “concomitant drugs” are met and the concomitant drug falls under “MTX” in “Drug code list_20171012.xlsx”, “unknown/unspecified” should be selected when the status of concomitant drugs is “unknown/unspecified”, and “without concomitant drug: methotrexate” should be selected otherwise.
Concomitant drug: corticosteroid	“With concomitant drug: corticosteroid” should be selected when the conditions for “concomitant drugs” are met and the concomitant drug falls under “steroid (oral + injection)” in “Drug code list_20171012.xlsx”, “unknown/unspecified” should be selected when the status of concomitant drugs is “unknown/unspecified”, and “without concomitant drug: corticosteroid” should be selected otherwise.
Concomitant drug: NSAIDs	“With concomitant drug: NSAIDs” should be selected when the conditions for “concomitant drugs” are met and the concomitant drug falls under “NSAIDs (oral + injection)” in “Drug code list_20171012.xlsx”, “unknown/unspecified” should be selected when the status of concomitant drugs is “unknown/unspecified”, and “without concomitant drug: NSAIDs” should be selected otherwise.
Concomitant drug: other DMARDs	“With concomitant drug: other DMARDs” should be selected when the drug meets the conditions for “concomitant drugs” and does not fall under “MTX” and falls under “DMARDs” in “Drug code list_20171012.xlsx”, “unknown/unspecified” should be selected when the status of concomitant drugs is “unknown/unspecified”, and “without concomitant drug: other DMARDs” should be selected otherwise.
Concomitant drug: Other drugs	“With concomitant drug: other drugs” should be selected when the drug meets the conditions for “concomitant drugs” and does not fall under “MTX”, “steroid (oral + injection)” or “DMARDs” in “Drug code list_20171012.xlsx”, “unknown/unspecified” should be selected when the status of concomitant drugs is “unknown/unspecified”, and

Name of data	Derivation and calculation methods

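### SAP 10.1 classes a listed drug record that cannot be placed in its date window as 'without' rather than 'unknown', so the drug-factor comparisons may be contaminated

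*SAP*

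**What the plan says.** Four rules act together.

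- **Incomplete dates (SAP 9.2).** "Dates including unknown date, month or year, or dates that cannot be true according to the calendar should be handled as" unknown, with no exceptions.
- **Missing data (SAP 9.1).** "Missing data will not be complemented, etc. during analysis", apart from items for which Chapter 10 or later defines a method. Chapter 10 defines none for the dates of drugs other than Humira.
- **Windows (SAP 10.1).** A previous medication must be "confirmed to have been administered between the start date of Humira treatment - 90 days and the start date of Humira treatment - 1 day". A concomitant drug must be listed in CRF section 5 or 6 "and confirmed to have been administered between the start date of Humira treatment and the end date of Humira treatment". An earlier biologic must be "confirmed to have been administered between the start date of a biological product and the start date of Humira" treatment minus one day. A second route admits biologics used in the 90 days before Humira.
- **Residual class (SAP 10.1).** Overall previous-medication status is unknown only when the CRF status field "is not specified or indeterminable, and “without previous medications” should be selected otherwise". For a single drug class, unknown applies only if the overall status is already unknown. For methotrexate the rule then ends "without concomitant drug: methotrexate” should be selected otherwise". Corticosteroids and other DMARDs follow the same pattern, and biologic history has the same form, tied to its own CRF field.

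For biologics, Protocol 8(3) item 3 collects "Presence/absence of history of biological therapy, name of drug, dose, duration (start date and end date), and reason for discontinuation".

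SAP 9.3 and 9.13 remove unknowns from the tests. SAP 11 already provides an 'unknown/unspecified' level for biologic history and for each methotrexate, corticosteroid, NSAID and other-DMARD status factor.

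**The concern.** The trigger for 'unknown' is in the wrong place. Whether a given drug was used in the window depends on that drug's record, but the unknown class depends on a patient-level field. A patient known to have a methotrexate record that cannot be placed in time is counted as a non-user instead of being set aside.

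Drug exposure is among the background factors tested against adverse reactions (Table 2.5.1), DAS28 remission (Table 3.1) and EULAR response (Table 3.5.2). The same classes are used in the background table (1.3) and in the tables split by methotrexate dose and by biologic history (2.11 and 2.12). These tables serve the survey's third purpose, finding factors that affect safety and efficacy. Table 2.5.5.X is produced only for factors with p < 0.05 in Table 2.5.1, so a diluted comparison can also drop a factor from the follow-up breakdown.

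**Working it through.** The plan states no figure on this point, so there is none to reproduce. The check has two parts: how the rules class particular patients, and how large the effect could be.

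**Part 1: the rules applied to four patients**

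1. *A fully dated NSAID during Humira treatment, plus methotrexate with no date that places it in the window.* The NSAID makes the overall status 'with concomitant drugs', which closes the unknown class for every drug. Methotrexate is not confirmed, so it falls to 'without'. However broadly 'indeterminable' is read, the result is the same, because the overall status is already settled.
2. *Methotrexate is the only listed drug, the status field is filled in, and no date is usable.* The field is specified, so on its plain wording the patient is 'without', both overall and for methotrexate. Only a broad reading of 'indeterminable' would give 'unknown'.
3. *Biologic history marked present, product named, start date given as a year only.* The window opens at the product's own start date, which SAP 9.2 has made unknown. An old course also fails the 90-day route. The field is filled in, so the literal result is 'without'. A remark in the same definition says the CRF section covers every biologic used previously, which allows the product to be counted.
4. *Methotrexate with a year-only start, but ongoing or with a complete stop date during Humira treatment.* Overlap can be shown despite the partial start, and nothing in SAP 10.1 forbids counting it. This patient need not be lost.

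Patient 1 is the firm case. Patients 2 and 3 depend on the reading.

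**Part 2: size**

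Inputs: N = 100 (Protocol 2). True users U = 30, 50 or 70, and the share u of users whose record is undecidable = 10, 20 or 30%, are assumptions; the documents give neither.

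Users moved to 'without': k = u × U. 
Contamination of the 'without' group: c = k / (N − U + k).

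| True users | u = 10% | u = 20% | u = 30% |
|---|---|---|---|
| 30 | 3/73 = 4% | 6/76 = 8% | 9/79 = 11% |
| 50 | 5/55 = 9% | 10/60 = 17% | 15/65 = 23% |
| 70 | 7/37 = 19% | 14/44 = 32% | 21/51 = 41% |

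If undecidable records are unrelated to outcome, the observed risk difference is the true one × (1 − c).

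For illustration, assume adverse-reaction rates of 40% in users and 15% in non-users, with u = 20%. With 70 users, the 'without' rate becomes (30 × 0.15 + 14 × 0.40)/44 = 10.1/44 = 23.0%, so the difference falls from 25 to 17.0 points. Exact power of the two-sided 5% Fisher test (SAP 9.13 and 9.14):

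| True users | Difference under literal rule | Power, literal rule | Power, undecidable set to unknown | Power, none undecidable |
|---|---|---|---|---|
| 30 | 23.0 points | 0.585 | 0.673 | 0.722 |
| 50 | 20.8 points | 0.587 | 0.736 | 0.758 |
| 70 | 17.0 points | 0.388 | 0.655 | 0.679 |

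Setting undecidable records to unknown keeps the difference at 25 points under the same assumption. At u = 0 the two rules agree.

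**The case against.** The best defence is that an incomplete date does not void a record. The SAP does not define 'confirmed' and does not require both dates to be complete. A complete date inside the window, an ongoing entry or a second dated record can each place the drug. This stands. A reader might infer that every partly dated record becomes 'without'; the text does not support that, and patient 4 shows why.

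For previous medications, Protocol 8(3) item 4 limits the CRF section to the three months before Humira, so listing there is already evidence of timing. That helps in part. SAP 10.1 still asks for confirmation on top of listing, and it also draws concomitant drugs from that same section, where listing cannot show use during Humira treatment.

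For biologics, the remark about all products previously used, and a broad reading of 'indeterminable', could avoid the wrong class. This also stands, so the biologic case is possible rather than certain.

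Protocol 6(3) item 7 lets the sponsor reinvestigate forms where needed. Queries may clear some or all of these records, but no rule covers those that remain.

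Finally, these are many unadjusted, exploratory comparisons in an uncontrolled survey. Only Tables 2.5.1, 3.1 and 3.5.2 test the factors; Tables 1.3, 2.11 and 2.12 are descriptive. That limits the consequence. It does not remove the wrong default, which applies to patient 1 on any reading.

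**Conclusion.** The gap is real. For methotrexate, corticosteroids and other DMARDs, a listed record that cannot be placed in the window is classed 'without' whenever another fully dated drug settles the overall status and, on the plain wording, whenever the status field is filled in. A listed biologic with a partial start date may go the same way. These patients stay in tests from which SAP 9.3 means to exclude unknowns.

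The comparisons may be contaminated. A reader might go further and conclude that they are contaminated, that differences certainly shrink, or that the reported share of users is certainly too low. The documents do not support this: they give no count of undecidable records, and queries may resolve some. Shrinkage toward zero also requires that such records be unrelated to outcome; otherwise the direction is open.

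The contamination ranges (4 to 11%, 9 to 23% and 19 to 41% for 30, 50 and 70 users) rest on an assumed 10 to 30% of users being undecidable. That share refers to records that cannot be placed in the window, a narrower group than all partly dated records. If there are none, the effect is zero. No primary hypothesis is touched, but the default is an explicit rule that can bias tested comparisons and is easy to change.

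**What to change.** Amend SAP 10.1:

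- **(a) Biologic history.** Take it from the CRF presence/absence field and the listed product, with no condition on the start date.
- **(b) Define 'confirmed'.** A record counts as 'with' if a complete date, an ongoing entry, or its earliest and latest possible dates show that it must overlap the window. It is ignored if it cannot overlap.
- **(c) Undecidable records.** If neither can be shown, and no other record confirms the class, set that drug class to 'unknown/unspecified' whatever the overall status. Report the number of such patients per class.

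SAP 9.2 needs a cross-reference, so that its blanket rule does not stop partial dates from being used in (b).

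The cost is SAP wording and a few lines of dataset code. No new data are needed, and the category already exists in SAP 11. The downside is that a few patients leave a test.

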### 9.3. Handling of unknown/unspecified

For calculation of percentage, the number of patients with “unknown” or “unspecified” data should be included in denominators. When a test is performed, patients with “unknown” or “undescribed” data should be excluded.

### 9.4. Handling of adverse events

For subtotals by System Organ Class (SOC), multiple events belonging to the same SOC in a single patient should be counted as 1 event. For subtotals by Preferred Term (PT), multiple events belonging to the same PT in a single patient should be counted as 1 event. SOC should be displayed in the order of international agreements, and PT should be displayed in the order of MedDRA/J code.

### 9.5. EULAR Response Criteria, Judgment criteria for DAS28

A method to calculate the absolute value of disease activity.

<Evaluation items>

(A) Number joints with tenderness

(a total of 28 joints from left and right shoulders, elbows, hands and knees)

(B) Number of swollen joints

[figure not shown]
(a total of 28 joints from left and right shoulders, elbows, hands and knees)

(C) Erythrocyte sedimentation rate (ESR) at 1 hour (mm)

(D) Overall disease activity (VAS) (mm)

(Assessment of the degree of overall disease activity of rheumatoid arthritis on a 10-cm line by the patient.)

(E) C-reactive protein (CRP) (mg/dL)

<Calculation formula when an ESR value is used>

$$\text{DAS28-4(ESR)} = 0.56 \times \sqrt{(A)} + 0.28 \times \sqrt{(B)} + 0.70 \times \ln(C) + 0.014 \times (D)$$

<Calculation formula when a CRP value is used>

$$\text{DAS28-4(CRP)} = 0.56 \times \sqrt{(A)} + 0.28 \times \sqrt{(B)} + 0.36 \times \ln((E \times 10) + 1) + 0.014 \times (D) + 0.96$$

### 9.6. Calculation formula for CDAI

CDAI score = tender joint count (28) + swollen joint count (28) + VAS by patient (cm) + VAS by doctor (cm)

### 9.7. Calculation formula for SDAI

SDAI score = tender joint count (28) + swollen joint count (28) + VAS by patient (cm) + VAS by doctor (cm) + CRP (mg/dL)

#### 9.8. Handling of patients transferred to another hospital

For patients transferred to another hospital, a person in charge of analysis will link and process CRF data based on information about patients transferred to another hospital received from DM in external file format. Analysis should be conducted with the use of data for which linking process has been completed.

#### 9.9. Descriptive statistics

The followings should be calculated for categorical data and quantitative data.

Type of data	Items to be calculated
Categorical data	Number of patients, percentage, etc.
Quantitative data	Number of patients, mean value, standard deviation, median value, minimum value, maximum value, first quartile, third quartile

#### 9.10. Basic rules for tabulation

Matter	Rule
Tabulation software	Microsoft Excel
Size of printed pages	It should be able to output analysis results onto A4 paper.
Composition	
The first sheet should be the cover page. The cover page should include the product name, survey title, type of analysis, and date created.
 
The second sheet should be a list of diagrams.
 
The list of diagrams should include diagram numbers, titles of analysis results, and analysis sets. *Provide link to corresponding figures.
 
On the third and subsequent sheets, diagrams should be created in the order presented in the list of diagrams (Sheet numbers should be diagram numbers).

Matters concerning spaces, punctuations, wording, etc.	
Punctuations: Two-byte punctuations should be “、” and “。”. One-byte punctuations should be “,” and “.”.
 
Katakana: All characters should be two-byte.
 
Alphabet: All characters should be one-byte, and a capital letter should be used at the beginning of a sentence where an alphabet is used.
 
Brackets: All brackets should be two-byte.
 
One-byte spaces
 
Space needed: Between a number and a unit, before and after “/” (other than units and fractions), before and after arithmetic symbols (+ - × ÷ =)
 
Space not needed: Between a number and %, before and after ~, before and after a slash “/” (units and fractions), a hyphen “-”

Diagram numbers and titles	
Diagram numbers should be based on “1” in the heading and starts from No. 1 in each figure and table in that heading (e.g. Tables 1.1, 1.2, etc.).
 
For all diagram numbers and titles, the font should be MS Mincho and the

Matter	Rule
	
font size should be 10.5 pt.
 
For all table titles in each Appended Form, the font should be MS Mincho and the font size should be 12 pt.
 
In all tables, the font should be MS Mincho and the font size should be 9 to 10.5 pt. In all footnotes, the font should be MS Mincho and the font size should be 9 pt.
 
Ruled lines should be 0.5-pt solid lines (double lines should not be used).
 
In all footnotes to figures, the font should be MS Mincho and the font size should be 9 pt.

Analysis set	The name of the analysis set and the number of patients included should be specified.
Footnotes	
Where it is considered necessary to provide an explanation in association with preparation of analysis results, provide the explanation in a footnote.
 
Footnotes should be in the following form:
 
Add a superscript “*sequential number” on the right side of a term, etc. that you want to explain, and provide the “*sequential number” corresponding to the footnote and the explanation under the diagram.

Percentage	
When a percentage is calculated, the denominator should be the number of patients in the analysis set.
 
*Specify in a footnote when the denominator used for calculation of a percentage in the same table is different from the number of patients in the analysis set.
 
When percentages for a breakdown of a factor or item are calculated, ensure that the total becomes 100%. Any item redundantly counted should be specified in a footnote.

Context of numbers	When a figure such as a patient composition figure is created, all numbers required to maintain consistency of the context of numbers should be provided.

